#### **6.6.1 Management of Hepatocellular Toxicity Associated with Cabozantinib/Placebo and Nivolumab/Ipilimumab**

Elevations of aminotransferases (ALT and AST) and bilirubin have been observed during treatment with cabozantinib, nivolumab, and ipilimumab. It is recommended that subjects with elevation of ALT, AST, and/or bilirubin have more frequent laboratory monitoring of these parameters. If possible, hepatotoxic concomitant medications should be discontinued in subjects who develop increased values of ALT, AST, or bilirubin, and other causes (eg, cancer-related, infection) should be evaluated.

CONFIDENTIAL

Protocol XL184-313 Protocol Amendment 3.0  
Page 85 of 193

The following condition requires discontinuation of all study drugs:

- Drug-related ALT or AST  $> 3 \times$  ULN in combination with total bilirubin  $> 2 \times$  ULN without reasonable other explanation, consistent with drug-induced liver injury (DILI).

[Table 6-3](#) provides suggested guidance on management of hepatotoxicity related to cabozantinib/placebo and nivolumab/ipilimumab.

In the event cabozantinib/placebo is interrupted and nivolumab/ipilimumab delayed due to an increase of serum ALT or AST  $> 3.0 \times$  ULN **or** serum total bilirubin  $>$  ULN to  $1.5 \times$  ULN, nivolumab and (if fewer than 4 ipilimumab doses have been administered and no AE has occurred that led to discontinuation of ipilimumab alone) ipilimumab should be resumed upon return of liver function tests to baseline grade, at which time cabozantinib/placebo should be resumed with a dose reduction (from either two tablets per day to one tablet per day, or one tablet per day to one tablet every other day, as appropriate).

If no additional ipilimumab is to be administered, the dose of cabozantinib/placebo should be re-escalated from one tablet per day to two tablets per day no sooner than 10 days after resumption of blinded oral therapy. Alternatively, if the subject had been taking one tablet every other day, then the dose of cabozantinib/placebo may be re-escalated to one tablet every day and, if tolerated, then to two tablets per day no sooner than 14 days thereafter.

Consult with the medical monitor to discuss further management should rechallenge be followed by any recurrence of increased liver function tests.

Dose delays should not alter the timing of other study assessments, including but not limited to tumor imaging scheduled based on W1D1 ( $\leq 3$  days after randomization).

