**Table 6-3: Suggested Management of Hepatotoxicity Associated with Study Treatment**

Severity of LFT a Elevations by Laboratory Value	Dose Modification Guidance b	Management/Follow-up Guidance
AST or ALT > ULN to 3.0 x ULN and/or total bili > ULN to 1.5 x ULN, regardless of baseline value	
 
Cabozantinib: 
 
Continue cabozantinib per protocol
 
 
 
Nivolumab /Ipilimumab: 
 
Continue therapy per protocol
 
 
 
	
 
Monitor LFTs per protocol.
 
Discontinue concomitant hepatotoxic medications, if possible.
 

AST or ALT > 3.0 x ULN to $\leq$ 5 x ULN or total bili > 1.5 x ULN to $\leq$ 3 x ULN, regardless of baseline value	
 
Cabozantinib: 
 
Interrupt cabozantinib dosing.
 
If LFTs return to baseline grade, resume cabozantinib at a reduced dose. After completion of ipilimumab regimen, re-escalate cabozantinib dose as per protocol. If no additional ipilimumab doses are to be administered, the dose of cabozantinib may be re-escalated no sooner than 10 days after re-initiation of cabozantinib.
 
See Section 6.6.1 for additional guidance.
 
 
 
Nivolumab /Ipilimumab: 
 
Delay therapy per protocol.
 
If LFTs return to baseline grade, resume therapy per protocol.
 
 
 
	
 
Monitor LFTs twice weekly or more frequently as deemed clinically necessary. 
 
If tapering off steroid therapy, monitor LFTs once weekly or more often per clinical judgmentc.
 
If LFTs return to baseline grade, resume with routine monitoring.
 
 
 
If LFT elevations persist > 3 days or worsen: 
 
Administer 0.5-1 mg/kg/day methylprednisolone or oral equivalent.
 
When LFTs return to baseline grade or CTCAE Grade <math>\leq</math> 1, taper steroids over at least 1 monthc.
 
Consider prophylactic antibiotics for opportunistic infections.
 
 
 

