AST or ALT > 5 x ULN or total bili > 3 x ULN, regardless of baseline value	
 
Cabozantinib: 
 
Discontinue cabozantinib if ALT or AST > 8 x ULN.
 
Otherwise interrupt cabozantinib dosing and resume at a reduced dose after LFTs return to baseline grade (Sponsor approval required)
 
 
 
Nivolumab /Ipilimumab: 
 
Delay dose or permanently discontinue.
 
 
 
	
 
Monitor LFTs twice weekly or more frequently as deemed clinically necessary.
 
During steroid taper, monitor LFTs once weekly or more often per clinical judgmentc.
 
For AST or ALT > 5 x ULN to <math>\leq</math> 20 x ULN, or total bilirubin > 3 x ULN to <math>\leq</math> 10 x ULN: 
 
Administer 1.0-2.0 mg/kg/day methylprednisolone IV or IV equivalent.
 
 
 
For AST or ALT > 20 x ULN, or total bilirubin > 10 x ULN: 
 
Administer 2.0 mg/kg/day methylprednisolone IV or IV equivalent.
 
 
 

CONFIDENTIAL

Severity of LFT a Elevations by Laboratory Value	Dose Modification Guidance b	Management/Follow-up Guidance
	
* In most cases of AST or ALT <math>> 5 \times</math> ULN, study treatment will be permanently discontinued. If the investigator determines a possible favorable benefit/risk ratio that warrants continuation of study treatment, a discussion between the investigator and the Medical Monitor/ designee must occur and approval from Medical Monitor prior to resuming therapy must be obtained.
	
 
• Add prophylactic antibiotics for opportunistic infections.
 
• Consult Gastroenterologist.
 
• If LFT elevations do not improve in <math>> 3</math> days, worsen or rebound: 
 
– Add mycophenolate mofetil 1g BID.
 
– If no response within an additional 3-5 days, consider other immunosuppressants per local guidelines.
 
 
 
• Dosing may resume when laboratory values return to baseline.
 
• Taper steroids over at least 1 monthc.
 

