#### **6.6.3.2.2 Criteria for Discontinuation of Nivolumab and Ipilimumab**

If a subject meets criteria for discontinuation and the investigator is unable to determine whether the event is related to one or both checkpoint inhibitors, the subject should discontinue both nivolumab and ipilimumab with the exception of certain cases of liver function test elevation (See [Section 6.6.1](#)).

Prior to re-initiating treatment in a participant with a dosing delay lasting  $> 12$  weeks, the Medical Monitor must be consulted. Tumor assessments should continue as per protocol even if dosing is delayed. Periodic study visits to assess safety and laboratory studies should also continue as clinically indicated during such dosing delays.

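### The restart rule in Protocol Section 6.6.1 for ALT/AST above 3.0 × ULN has no upper limit and no approval step, while Table 6-3 confines that rule to 5 × ULN and requires approval to resume above it

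*Protocol*

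**What the plan says.** The restart paragraph of Protocol Section 6.6.1 opens with its trigger: "In the event cabozantinib/placebo is interrupted and nivolumab/ipilimumab delayed due to an increase of serum ALT or AST" above 3.0 × ULN, or for total bilirubin between ULN and 1.5 × ULN. It then directs that nivolumab and (if fewer than four doses have been given and no adverse event has stopped it alone) "ipilimumab should be resumed upon return of liver function tests to baseline grade, at which time cabozantinib/placebo should be resumed with a dose reduction". The Medical Monitor appears only afterwards: "Consult with the medical monitor to discuss further management should rechallenge be followed by any recurrence of increased liver function tests". A separate rule earlier in the section stops all drugs when drug-related ALT or AST above 3 × ULN occurs together with bilirubin above 2 × ULN and no other reasonable explanation.

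Table 6-3 grades the response by peak value.

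- **> 3.0 to ≤ 5 × ULN (or bilirubin > 1.5 to ≤ 3 × ULN).** For the oral drug: "If LFTs return to baseline grade, resume cabozantinib at a reduced dose". Nivolumab and ipilimumab are delayed and also resume at baseline grade. No approval is mentioned.
- **> 5 × ULN (or bilirubin > 3 × ULN).** The oral drug is discontinued if ALT or AST exceeds 8 × ULN. For the rest: "Otherwise interrupt cabozantinib dosing and resume at a reduced dose after LFTs return to baseline grade (Sponsor approval required". For nivolumab and ipilimumab: "Delay dose or permanently discontinue". A note adds that AST or ALT above 5 × ULN leads to permanent discontinuation in most cases, and that if the investigator sees grounds to continue, "approval from Medical Monitor prior to resuming therapy must be obtained".

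**The concern.** The paragraph and the table give different instructions to the same reader for the same subject. Someone held with an isolated transaminase rise above 5 × ULN meets the paragraph's trigger as written. The paragraph then says to restart at baseline grade, while the table says treatment usually ends and otherwise restarts only after approval.

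What is at stake is the safety of rechallenge. Prior review by the Medical Monitor or Sponsor is the table's safeguard for the higher elevations, and the paragraph omits it. Liver events were prominent among the reasons for stopping in the earlier triplet cohort described in Protocol Section 1.6: adverse events led to discontinuation in 9 of 44 subjects, with ALT increased listed 4 times and AST increased 3 times (terms overlap). The SAP (Section 8.6 and Table 16) plans recurrence-after-rechallenge summaries for ALT/AST above 3 × and above 10 × ULN. Those summaries would be harder to read if sites applied different restart rules.

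**Working it through.** No arithmetic applies, so the check sets the two texts side by side. Take a subject with an isolated ALT/AST rise, all drugs held, and liver tests back to baseline grade.

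| Peak ALT/AST | Section 6.6.1 paragraph | Table 6-3 | Match |
|---|---|---|---|
| > 3 to ≤ 5 × ULN | Resume; oral drug at reduced dose; no approval | Same | Yes |
| > 5 to ≤ 8 × ULN | Same instruction | Permanent stop in most cases; otherwise resume only with approval | No |
| > 8 × ULN | Same instruction, oral drug included | Oral drug discontinued; nivolumab/ipilimumab delayed or discontinued, and resumed only with approval | No |

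1. **Can a subject above 5 × ULN meet the trigger?** Yes. The table allows interruption and delay in that row, and the paragraph's only ALT/AST condition is a value above 3.0 × ULN. A subject first held at 4 × ULN whose ALT later peaks above 5 or 8 × ULN also meets it.
2. **Does another rule in Section 6.6.1 close the gap?** The stop rule for drug-induced liver injury needs bilirubin above 2 × ULN as well, so isolated transaminase elevations fall outside it.
3. **Does a general rule close it?** Sections 3.6.1, 6.6 and 6.6.3.2.1 require Sponsor approval after more than 12 weeks without any study treatment. That depends on duration, not on the size of the elevation.
4. **Does the protocol say the table overrides the text?** No. Section 6.6.1 and the table's title both present it as suggested management, while the paragraph says treatment *should* be resumed.
5. **Do the cross-references settle it?** Only in part. In the table, only the > 3 to ≤ 5 × ULN row points back to Section 6.6.1, and Section 6.6.3.2 names Table 6-3. But Sections 6.6 and 6.6.3 send sites to Section 6.6.1 as a whole. Section 6.6.3.2.2 also refers there for its liver exception to stopping both checkpoint inhibitors when causality is unclear: "the subject should discontinue both nivolumab and ipilimumab with the exception of certain cases of liver function test elevation".
6. **Is the trigger sentence otherwise sound?** No. Its bilirubin band, > ULN to 1.5 × ULN, is the one in which Table 6-3 continues all drugs. The hold band is > 1.5 to ≤ 3 × ULN. The sentence therefore fails to match the table's hold row for both bilirubin and transaminases.

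The paragraph after the restart rule says the oral dose *should* be re-escalated if no ipilimumab remains to be given, where the table says it *may* be. With no upper limit on the restart rule, that wording also reaches subjects who peaked above 5 × ULN.

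**The case against.** The strongest reply is that the paragraph merely elaborates the > 3 to ≤ 5 × ULN row. Table 6-3 is cited immediately before it, only that row refers back to it, and the two share the same content on reduced dose and the 10-day wait. On this reading a subject above 8 × ULN has been discontinued from the oral drug rather than interrupted, so the paragraph is never triggered. Between 5 and 8 × ULN the paragraph is silent on approval rather than dispensing with it, and a site can satisfy both texts by seeking approval. There are also other checks. Hepatitis, including ALT/AST above 10 × ULN, is reportable within 24 hours (Section 8.3 and Table 8-1). Above 5 × ULN the table calls for steroids, a gastroenterology consultation and a taper of at least one month. Checkpoint inhibitors cannot resume until steroids are at or below 10 mg/day prednisone equivalent (Section 6.6.3.2.1).

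Much of this stands as evidence of intent, and it makes an unreviewed restart less likely. A site that applies the table's stop rule will not restart the oral drug above 8 × ULN; that error needs a site working from the text alone. But intent is not stated where the site reads the rule. An instruction that treatment should be resumed does not sit with permanent discontinuation in most cases. Reporting an event and treating it are not approval before rechallenge.

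**Conclusion.** The concern holds. The Section 6.6.1 restart paragraph is wrong as written: it matches Table 6-3 in one of three ALT/AST bands above 3 × ULN. It omits the approval step from > 5 to 8 × ULN and, read alone, permits an oral-drug restart above 8 × ULN, where the table says stop. This assumes that the table states the intended rule, which the cross-references support, and that some sites will work from the paragraph. How many subjects would be affected cannot be estimated: Section 1.6 gives no ULN multiples for the earlier cohort and nothing on restarts. No efficacy endpoint is threatened. The wording should be corrected on safety grounds.

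**What to change.** Limit the restart paragraph in Protocol Section 6.6.1 to ALT/AST > 3.0 to ≤ 5 × ULN and change its bilirubin band to > 1.5 to ≤ 3 × ULN, so that it matches the hold row of Table 6-3. Add one sentence stating that above 5 × ULN Table 6-3 governs: permanent discontinuation in most cases, Medical Monitor/Sponsor approval before any resumption, and discontinuation of cabozantinib/placebo above 8 × ULN. Align the *should*/*may* re-escalation wording in the same edit. The cost is one paragraph of protocol text and a clarification memo to sites. Endpoints, data collection and sample size are unaffected.

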**Table 6-3: Suggested Management of Hepatotoxicity Associated with Study Treatment**

Severity of LFT a Elevations by Laboratory Value	Dose Modification Guidance b	Management/Follow-up Guidance
AST or ALT > ULN to 3.0 x ULN and/or total bili > ULN to 1.5 x ULN, regardless of baseline value	
 
Cabozantinib: 
 
Continue cabozantinib per protocol
 
 
 
Nivolumab /Ipilimumab: 
 
Continue therapy per protocol
 
 
 
	
 
Monitor LFTs per protocol.
 
Discontinue concomitant hepatotoxic medications, if possible.
 

AST or ALT > 3.0 x ULN to $\leq$ 5 x ULN or total bili > 1.5 x ULN to $\leq$ 3 x ULN, regardless of baseline value	
 
Cabozantinib: 
 
Interrupt cabozantinib dosing.
 
If LFTs return to baseline grade, resume cabozantinib at a reduced dose. After completion of ipilimumab regimen, re-escalate cabozantinib dose as per protocol. If no additional ipilimumab doses are to be administered, the dose of cabozantinib may be re-escalated no sooner than 10 days after re-initiation of cabozantinib.
 
See Section 6.6.1 for additional guidance.
 
 
 
Nivolumab /Ipilimumab: 
 
Delay therapy per protocol.
 
If LFTs return to baseline grade, resume therapy per protocol.
 
 
 
	
 
Monitor LFTs twice weekly or more frequently as deemed clinically necessary. 
 
If tapering off steroid therapy, monitor LFTs once weekly or more often per clinical judgmentc.
 
If LFTs return to baseline grade, resume with routine monitoring.
 
 
 
If LFT elevations persist > 3 days or worsen: 
 
Administer 0.5-1 mg/kg/day methylprednisolone or oral equivalent.
 
When LFTs return to baseline grade or CTCAE Grade <math>\leq</math> 1, taper steroids over at least 1 monthc.
 
Consider prophylactic antibiotics for opportunistic infections.
 
 
 

AST or ALT > 5 x ULN or total bili > 3 x ULN, regardless of baseline value	
 
Cabozantinib: 
 
Discontinue cabozantinib if ALT or AST > 8 x ULN.
 
Otherwise interrupt cabozantinib dosing and resume at a reduced dose after LFTs return to baseline grade (Sponsor approval required)
 
 
 
Nivolumab /Ipilimumab: 
 
Delay dose or permanently discontinue.
 
 
 
	
 
Monitor LFTs twice weekly or more frequently as deemed clinically necessary.
 
During steroid taper, monitor LFTs once weekly or more often per clinical judgmentc.
 
For AST or ALT > 5 x ULN to <math>\leq</math> 20 x ULN, or total bilirubin > 3 x ULN to <math>\leq</math> 10 x ULN: 
 
Administer 1.0-2.0 mg/kg/day methylprednisolone IV or IV equivalent.
 
 
 
For AST or ALT > 20 x ULN, or total bilirubin > 10 x ULN: 
 
Administer 2.0 mg/kg/day methylprednisolone IV or IV equivalent.
 
 
 

CONFIDENTIAL

Severity of LFT a Elevations by Laboratory Value	Dose Modification Guidance b	Management/Follow-up Guidance
	
* In most cases of AST or ALT <math>> 5 \times</math> ULN, study treatment will be permanently discontinued. If the investigator determines a possible favorable benefit/risk ratio that warrants continuation of study treatment, a discussion between the investigator and the Medical Monitor/ designee must occur and approval from Medical Monitor prior to resuming therapy must be obtained.
	
 
• Add prophylactic antibiotics for opportunistic infections.
 
• Consult Gastroenterologist.
 
• If LFT elevations do not improve in <math>> 3</math> days, worsen or rebound: 
 
– Add mycophenolate mofetil 1g BID.
 
– If no response within an additional 3-5 days, consider other immunosuppressants per local guidelines.
 
 
 
• Dosing may resume when laboratory values return to baseline.
 
• Taper steroids over at least 1 monthc.
 

ALT or AST $> 3 \times$ ULN AND total bilirubin $> 2 \times$ ULN AND no radiographic evidence of biliary obstruction	
 
• All study drugs must be discontinued.
 
	
 
• Follow the above management/follow-up guidance by grade.
 

ALT, alanine aminotransferase; AST, aspartate aminotransferase; bili, bilirubin; CTCAE, Common Terminology Criteria for Adverse Events; IV, intravenous; LFT, liver function tests; ULN, upper limit of normal

a LFTs include AST, ALT and total bilirubin.

b For brevity, the term “cabozantinib” refers to blinded oral study treatment of cabozantinib or cabozantinib-matched placebo.

c Subjects on IV steroids may be switched to an equivalent dose of oral corticosteroids (eg, prednisone) at start of tapering or earlier, once sustained clinical improvement is observed. Lower bioavailability should be taken into account when switching to the equivalent dose of oral corticosteroids.

## 6.6.2 Management of AEs Associated with Cabozantinib/Placebo

Throughout the remainder of [Section 6](#) the term “cabozantinib” refers to blinded oral study treatment of cabozantinib or cabozantinib-matched placebo. Considerations for management of AEs associated with oral study medication are presented below.

- The assigned dose for cabozantinib is 40 mg qd.
- Two dose reduction levels of cabozantinib (20 mg qd and 20 mg every other day [qod]) are permitted (see [Table 6-4](#)).

CONFIDENTIAL

Protocol XL184-313 Protocol Amendment 3.0  
Page 88 of 193

- Dose modification criteria for treatment-related AEs of cabozantinib are shown in [Table 6-5](#). Grade 1 and tolerable Grade 2 AEs are managed similarly; Grade 3 and intolerable Grade 2 AEs are managed similarly.
- Dose reinstitution and reescalation after dose interruptions and/or reductions:
  - If the subject recovers from his or her toxicities to CTCAE v5  $\leq$  Grade 1 or to the baseline value (or lower) and the AE was unrelated to oral study medication, then oral study medication may be restarted with no change in dose.
  - If the subject recovers from his or her toxicities to  $\leq$  Grade 1 or to the baseline value (or lower) and the AE was deemed related to oral study medication, then cabozantinib may be reinitiated but this must be at a reduced dose (see [Table 6-4](#)).
  - Subjects receiving a dose of 20 mg every other day (qod) may be restarted at the same dose if deemed safe at the discretion of the Investigator. Subjects unable to tolerate a dose of 20 mg qod must discontinue cabozantinib/placebo upon discussion with the Sponsor.
  - Re-escalation to the previous dose may be allowed at the discretion of the Investigator but no sooner than 10 days beyond improvement of AEs that led to the dose reduction to Grade 1 (or baseline value), as long as AEs are deemed tolerable and easily managed by optimized supportive treatment. Dose reescalation is not allowed following a cabozantinib-related dose reduction for Grade 4 hematologic toxicities or Grade 4 AEs affecting major organs (eg, central nervous system [CNS], cardiac, hepatic, renal, pulmonary GI).
- Guidelines for the management of specific AEs of cabozantinib such as GI disorders, non-GI fistula formation, hemorrhage, thromboembolic events, hypertension, stomatitis and mucositis, skin disorders, osteonecrosis, proteinuria, nervous system disorders, infections and infestations, blood system disorders, fatigue, weight loss, QTc prolongation, electrolyte disorders, endocrine disorders, and respiratory disorders are provided in [Section 6.6.2.1](#).

CONFIDENTIAL

Protocol XL184-313 Protocol Amendment 3.0  
Page 89 of 193

**Table 6-4: Dose Reductions of Cabozantinib (Oral Dosing)**

First Dose Level Reduction	Second Dose Level Reduction
20 mg daily (qd)	20 mg every other day (qod)

Cabozantinib must be discontinued upon discussion with the Sponsor if a dose of 20-mg cabozantinib every other day (minimum dose) is not tolerated.

**Table 6-5: Dose Modifications for Cabozantinib-Related AEs**

CTCAE v5 Grade	Recommended Guidelines for Management
Grade 1 AEs	Add supportive care as indicated. Continue cabozantinib at the current dose level if AE is manageable and tolerable.
Grade 2 AEs that are tolerable and are easily managed	Continue cabozantinib at the current dose level with supportive care.
Grade 2 AEs that are intolerable and cannot be adequately managed	Cabozantinib should be dose reduced or interrupted. Note: It is recommended that dose interruptions be as brief as possible.
Grade 3 AEs (except clinically non-relevant laboratory abnormalities)	Cabozantinib should be interrupted unless the toxicity can be easily managed with a dose reduction of cabozantinib and optimal medical care. Note: It is recommended that dose interruptions be as brief as possible.
Grade 4 AEs (except clinically non-relevant laboratory abnormalities)	Cabozantinib must be interrupted immediately. In general, cabozantinib should be discontinued unless the following criteria are met: 

• Subject is deriving clear clinical benefit as determined by the Investigator and agreed by the Sponsor

• Toxicity can be managed with a dose reduction of cabozantinib following recovery to Grade 1 (or baseline value) and optimal medical care

 Sponsor must be contacted to discuss treatment continuation upon resolution of AEs.

AE, adverse event.

Note: Cabozantinib dose modification criteria for specific medical conditions are provided in [Section 6.6.2.1](#).

CONFIDENTIAL

Protocol XL184-313 Protocol Amendment 3.0  
Page 90 of 193

